# 5.3.3 Use of conservators

The preservatives are used in order to inhibit microbial growth and suppress biodegradation inside medicines. [32] A great variety of conservatives have been used throughout history. The chronic use of drugs has been linked to irritation and alterations of the ocular surface, it has been established that the conservatives themselves have adverse events, which are attached to those of the active principle that preserve. [33]

The preservatives are classified into detergents and oxidants, and a more recent version of oxidants called buffered by ions. [32] The BAK is the most historically used preservative, belongs to the class of detergents. The reasons for its popularity include its broad spectrum of action and its familiarity with the formulator industry.

Although its effectiveness is well recognized, there are numerous studies documenting the harmful effects of BAK. BAK at concentrations of 0.05-0.1% induces necrosis and concentrations of 0.01% apoptosis. Its effects are cumulative and become more severe at higher concentration and with more frequent exposures. [32] [34] [35] It has been postulated that the presence of BAK is responsible for changes in the conjunctival surface identified by cytology by impression, such as the decrease in the density of goblet cells. [36] [37]

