# 5.5.3 Hypothesis

Ha The ophthalmic solution PRO-087 presents a safety and tolerability profile similar to comparators in healthy subjects

*Ho The ophthalmic solution PRO-087 presents a different safety and tolerability profile compared to comparators in healthy subjects.* 

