#### 6.6.1 Calculation of the sample size.

Although there are no references on the calculation of sample size in phase I studies, it was considered pertinent to perform it according to the presentation of adverse events reported by Hwang HS, et al, in a case-control study in 150 subjects with ophthalmic solutions with Hyaluronate sodium and diquafosol with and without preservative for 3 months. [46].

The percentage of adverse events that occurred with the preservative-free HS solution was 8%, which is why we consider that at least more than 60% of the exposed subjects will not present this rate of adverse events.

The sample size was calculated using the formula for proportions

$$n = \left[ (p1)(p2) + (p1)(p2) \left( \frac{Z_{1-\alpha}}{2} + Z_{1-\beta} \right)^2 \right] / (p1 - p2)^2$$

With a statistical confidence of 95% corresponding to the type I error, equal to 1.96, with a power of 80%, corresponding to the type II error, equal 0.84.

According to the previous calculation, the result is 7.6 subjects (8) per group. The total when considering 3 intervention groups is 24 subjects, which was increased by 25% due to the probable losses. The total sample size required is 30 subjects. Therefore, each group will consist of 10 subjects, who will provide both eyes for the analysis, so that the total sample to be analyzed will be composed of 60 eyes.

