# 8.3 Statistical methodology

#### 8.3.1 Analysis of primary and secondary outcome variables.

The statistical analysis will be carried out by personnel from Sophia Laboratories, S.A. of C.V The statistical program SPSS version 19 (IBM Corporation, Armonk, NY, USA) will be used.

The designated personnel will be blinded to the intervention groups. The coding will be done using consecutive numbers for each intervention group.

The data will be collected and sorted in an excel sheet. Later they will be exported to the platform of the SPSS program. The variables will be categorized according to their nature.

CONFIDENTIAL

The result of the continuous quantitative variables will be presented in measures of central tendency: media, standard deviation and ranges. **See Table 5**. Scales to be used

The normal distribution of the results will be obtained by the Kolmogorov-Smirnov test.

The statistical analysis of the continuous **quantitative variables** to find significant differences (p) will be the following:

- Intra-group analysis: Wilcoxon rank test.
- Inter-group analysis: Kruskal-Wallis test.

The level of difference to consider significance will be an alpha of 0.05 or less.

The result of nominal and ordinal qualitative variables will be presented in frequencies, proportions and percentages. See table 1 (section 6.4.3).

The statistical analysis to identify significant differences of the **qualitative variables** will be done by creating 2x2 contingency tables and will be done as follows:

- • Intra-group difference: McNemar test.
- • Difference between groups: χ2 test (Chi-square) of Pearson.
- The level of difference to consider significance will be of an alpha of 0.05 or less.
- For the reporting of adverse events all eyes of those participants who were randomly assigned to an intervention group after the baseline visit will be considered. The results will be expressed in number of cases (eyes).
- The final report of the results will be shown in tables or graphs, as appropriate.
- It will be considered that the investigational drug is safe and tolerable when there are no clinical and statistical differences in all the variables of primary outcome, with respect to its comparators.

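### The rule for calling PRO-087 safe and tolerable ignores the direction of a difference, so a significant and clinically relevant advantage withholds the conclusion exactly as an equal harm would

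*Combined protocol and SAP*

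**What the plan says.** - **Decision rule (8.3.1, last part).** The investigational drug is considered "safe and tolerable when there are no clinical and statistical differences in all the variables of primary outcome, with respect to its comparators". No word in the rule limits it to unfavourable differences, no margin is given, and a clinical difference is not defined.
- **Hypotheses (5.5.3).** Ha reads "The ophthalmic solution PRO-087 presents a safety and tolerability profile similar to comparators in healthy subjects". Ho reads "The ophthalmic solution PRO-087 presents a different safety and tolerability profile compared to comparators in healthy subjects". A better profile and a worse one both fall under Ho.
- **Tests (8.3.1).** For quantitative variables, "Inter-group analysis: Kruskal-Wallis test". For qualitative variables, in 2x2 tables, "Difference between groups: χ2 test (Chi-square) of Pearson". The threshold is "The level of difference to consider significance will be an alpha of 0.05 or less".
- **Primary variables (6.4.1.1 and 6.4.1.2).** Goblet cell density, adverse events, intraocular pressure, visual ability, laboratory tests, epithelial defects, hyperaemia and chemosis; for tolerability, burning, foreign body sensation, itching and the eye comfort index.
- **Direction of harm.** For most of these the protocol already implies it. Table 5 gives absence as normal for chemosis, burning, foreign body sensation, pruritus and adverse events, the normal grade for hyperaemia, and more than 500 cells per square millimetre for goblet cells. The Nelson and Oxford scales are ordered by severity.

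No other section says how a difference in PRO-087's favour is to be handled.

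**The concern.** A safety and tolerability verdict should separate harm from benefit. This rule uses only whether the arms differ, and discards the direction that the protocol's own scales supply. If PRO-087 caused clearly less burning than its comparators, the prespecified route to the favourable conclusion would be closed, on the same terms as if it caused clearly more.

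The protocol's rationale makes an advantage conceivable. Section 5.3.3 links the preservative BAK to conjunctival changes, "such as the decrease in the density of goblet cells", and 5.4 justifies PRO-087 by the absence of preservative.

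Two outcomes are at stake. Either a favourable result leaves the main conclusion unsupported, or the sponsor sets the rule aside after seeing the results, which defeats the purpose of prespecifying it. Pairwise tests or a multiplicity adjustment alone would not cure this, because a two-sided pairwise test read only as significant or not is just as blind to direction.

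**Working it through.** The plan gives no figure for how this rule performs. Its only design figure, the sample size in 6.6.1, does not enter the argument. The check uses 10 subjects per arm (6.6), three arms, the tests named in 8.3.1 and alpha 0.05. All effect sizes below are assumptions, because the documents give no SD, margin or symptom rate for the comparators.

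**1. Mirror-image counts.** Take a yes/no symptom in 0/10 on PRO-087, 5/10 on one comparator and 5/10 on the other. In all, 10 of 30 have it, so each arm expects 10/3 with and 20/3 without.

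- PRO-087 arm: (0 − 3.333)²/3.333 + (10 − 6.667)²/6.667 = 3.333 + 1.667 = 5.0
- Each comparator: (5 − 3.333)²/3.333 + (5 − 6.667)²/6.667 = 0.833 + 0.417 = 1.25
- Sum: 5.0 + 2 × 1.25 = 7.5 on 2 df, p = 0.0235

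Now take 10/10 against 5/10 and 5/10. This is the same table with yes and no exchanged, so chi-square is again 7.5 and p = 0.0235. In the 2x2 form that 8.3.1 specifies, 0/10 against 5/10 and 10/10 against 5/10 both give chi-square 6.67, p = 0.0098. The rule receives the same input for the best and the worst result.

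**2. Continuous variables.** Simulated Kruskal-Wallis with 10 per arm, normal data, equal comparators and PRO-087 shifted (10,000 runs):

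| True shift of PRO-087 | Rejects, shift favourable | Rejects, shift unfavourable |
|---|---|---|
| 0 | 0.045 | – |
| 1.0 SD | 0.54 | 0.54 |
| 1.5 SD | 0.89 | 0.89 |

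This applies to variables that Table 5 types as continuous, such as goblet cell density. It does not apply to burning, foreign body sensation and pruritus, which Table 5 types as nominal and 8.3.1 sends to chi-square.

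**3. How often a symptom would count against PRO-087 for being better.** Exact enumeration of the uncorrected 2x2 Pearson test, 10 per arm, one symptom, one comparator: the probability of every table with p ≤ 0.05 and fewer cases on PRO-087 is summed.

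| True rate, PRO-087 vs comparator | Significant in PRO-087's favour |
|---|---|
| 0% vs 8% | 0.6% |
| 5% vs 20% | 7% |
| 10% vs 30% | 14% |
| 10% vs 60% | 66% |

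The 8% is the only event rate in the documents. It is an adverse-event rate from the study cited in 6.6.1, used here for scale only. An observed 0/10 against 3/10 gives p = 0.060 and would not trigger the rule. If both eyes were analysed as independent (20 per arm), 5% versus 20% would rise from 7% to 29%.

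**4. Effect of making the rule directional.** Pairwise normal approximation, 10 per arm, assumed 1 SD shift: 1/√(2/10) = 2.236.

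- Two-sided 0.05, chance that a 1 SD benefit counts against PRO-087: Φ(2.236 − 1.96) = Φ(0.276) = 0.61
- Worse-only at one-sided 0.025, same benefit: Φ(−2.236 − 1.96) = Φ(−4.196), about 0.00001
- Worse-only, chance that a 1 SD harm is flagged: Φ(0.276) = 0.61, unchanged

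On this approximation nothing is lost in detecting harm.

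**The case against.** Several points on the other side have force.

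- **The rule has a clinical limb.** It speaks of clinical and statistical differences. If both are needed, a significant but trivial advantage does no damage, and every percentage based on p-values alone is an upper bound. This stands. It does not rescue the rule: an advantage that is both significant and clinically relevant still counts as a difference, and the undefined clinical limb is nowhere said to carry direction.
- **Withheld is not reversed.** A reader might infer that a better PRO-087 would be declared unsafe. The documents do not support that. Section 8.3.1 says when the product is considered safe and tolerable and states no verdict otherwise; Ho in 5.5.3 speaks only of a different profile. The result would be an unsupported conclusion, not a finding of harm. Summary statistics by arm are also to be reported, so the direction would be visible.
- **Healthy eyes leave little room to improve.** Subjects are 18 to 40 years old and ophthalmologically healthy (6.2.1), and normal values are mostly absence. This stands, and it lowers the likely frequency. Drops can still cause symptoms after instillation, which the diary collects (6.4.3.9).
- **The preservative argument is limited.** A reader might infer that Systane Ultra contains a preservative and that PRO-087 should therefore beat it. The documents do not say so. Xyel Ofteno is described as preservative-free, 5.3.3 and 5.4 concern BAK and cumulative exposure, treatment lasts 10 days, and 5.2 states that no lubricant has been shown better than another. The rationale makes an advantage possible; it does not make one likely over both comparators.
- **The error is conservative.** It hides no harm, the trial is exploratory, and the stopping criteria in 9.2 do not rely on this rule. This limits the severity, but the rule remains the stated basis for the trial's main conclusion.

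**Conclusion.** The point holds. As written in 8.3.1 and echoed in 5.5.3, the criterion cannot tell benefit from harm. A significant and clinically relevant difference in PRO-087's favour on any primary variable withholds the safe-and-tolerable conclusion on the same terms as an equal harm. That follows from the wording and the tests, and the mirror-image tables show it without any assumed effect.

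The frequency is uncertain: from under 1% to about two thirds of trials for one symptom and one comparator over the rates examined, and probably towards the low end in healthy eyes. The figures assume 10 independent subjects per arm, and they are upper bounds if the clinical limb must also be met. The consequence is a favourable conclusion lost or argued for afterwards; no subject is put at risk. The rule merits correction because the correction is cheap.

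**What to change.** Before unblinding:

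- **State the unfavourable direction for each primary variable in 8.3.1.** Lower for goblet cell density and visual ability. Higher for staining, hyperaemia, chemosis, burning, foreign body sensation, itching, comfort index score and adverse events. Two-sided for laboratory values and for intraocular pressure, for which Table 5 gives a lower and an upper limit.
- **Judge it on contrasts of PRO-087 with each comparator,** with estimates and confidence intervals. The omnibus Kruskal-Wallis test has no sign and can also reject because the two comparators differ from each other.
- **Let only an unfavourable difference count against the conclusion.** Report favourable differences without letting them withhold it.
- **Reword 5.5.3** so that the opposing hypothesis is a worse profile, not a different one.
- **Limit the claim.** Unless a margin is prespecified, the conclusion is that no unfavourable difference was detected. With 10 per arm, a non-significant result does not demonstrate non-inferiority.

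The cost is a few added pairwise contrasts and the loss of the word similar from the claim. No extra subjects, visits or measurements are needed.

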#### 8.3.2 Additional analyzes

A partial analysis will be carried out with the objective of evaluating safety and adherence once 3 subjects per group (33% of the sample size) have completed all the visits and study procedures. Non-parametric statistics will be used and the same mechanisms described for the total analysis of the data will be used.

#### 8.3.3 Population analysis and management of missing data

An intention-to-treat analysis will be carried out, which will include the data of the participants who have completed at least two visits (Visit 1 and 2), after the baseline visit.

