#### 6.2.2.2 Medical and therapeutic criteria

#### 6.2.3 Elimination criteria

- Withdrawal of the consent letter under information.
- Presentation of serious adverse event.
- No tolerability or hypersensitivity to any of the compounds used during the tests (fluorescein, green lysine, tetracaine)
- No tolerability or hypersensitivity to any of the investigational drugs.
- Adherence <50% determined by the diary of the subject or by the weight of the bottle, of the established dose of the pharmacological intervention in any of the visits.

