#### 6.3.2.1 Procedure to monitor adherence

Before delivering the medication to the research subject, the pharmacist must carry out the weighing of the bottles to be delivered. After the return of the medication by the subject will also carry out the weighing. Guidelines to follow for weighing:

- The pharmacist will use the scale provided by the sponsor
- Place the bottle in the center of the scale. You will get the result of the measurement.
- Remove the jar from the balance and put it back in, confirming that the measurement is the same. If it is different, it will weigh one more time and take the average of the 3 measurements
- Record the result in the log and the CRF provided by the sponsor

The adhesion will be calculated considering: the weight of the empty bottle, the weight of the drop, the weight of the bottle with the content, the calculation of the total of drops to be applied during the entire time of intervention and the total weight of the drops applied. The following simplified formula will be used:

$$Ad = \frac{\left(P_i - P_f\right)100}{P_T}$$

Where:

Ad = Adhesion

 $P_i$  = weight of the bottle delivered to the subject at the start

 $P_f$  = weight of the bottle returned by the subject

 $P_T$  = weight of the posology indicated for the intervention

$$P_T = (P_g)G$$

Where:

 $P_g$  = weight of the intervention drop, determined by the research and development department G = number of drops indicated for the intervention

Adherence will be estimated at each visit where the research subject returns the intervention. Only those bottles without apparent physical damage will be considered for the calculation. This result will allow the PI to determine if the subject continues in the study according to the stipulations of the elimination criteria.

The evaluation of the adherence by means of the diary of the subject will be carried out in the following way:

$$Ad = (A_r)100/A_i$$

*Ad* = Adherence

 $A_r$  = Registered applications

 $A_i$  = Applications indicated for the intervention

The final (overall) adhesion will be determined by the average of the adherence of each of the visits.

It will not be considered for the calculation of final adherence if the subject did not return the bottle in two subsequent visits.

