- Those subjects who comply with an adherence greater than 60% will be included in the statistical analysis to meet the objective of the study. It was considered that from the minimum dose necessary to obtain a pharmacological effect and the presence of adverse events (exposure) is sufficient to fulfill the general objective of the design, according to the pharmacological characteristics of the product under investigation.

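### The set called intention-to-treat requires Visits 1 and 2, so where it governs, subjects who leave early for intolerance are excluded from the symptom and sign primaries

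*Combined protocol and SAP*

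**What the plan says.** Three rules in the combined protocol and SAP decide who is analysed.

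- Section 8.3.3 announces an intention-to-treat analysis "which will include the data of the participants who have completed at least two visits (Visit 1 and 2), after the baseline visit". Its heading also promises handling of missing data, but the section gives no rule for it.
- Section 8.3.1 adds an adherence filter: "Those subjects who comply with an adherence greater than 60% will be included in the statistical analysis to meet the objective of the study".
- Section 8.3.1 uses the full randomised set for one purpose only: "For the reporting of adverse events all eyes of those participants who were randomly assigned to an intervention group" are to be counted.

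Section 6.2.3 lists the ways out of the study. They include a serious adverse event, "No tolerability or hypersensitivity to any of the investigational drugs", and "Adherence <50% determined by the diary of the subject or by the weight of the bottle" at any visit.

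The conclusion rule is in section 8.3.1: "It will be considered that the investigational drug is safe and tolerable when there are no clinical and statistical differences in all the variables". The rule is confined to the primaries and is judged relative to the comparators. Sections 6.4.1.1 and 6.4.1.2 list those primaries. They include adverse events, epithelial defects, hyperemia and chemosis for safety, and burning, foreign body sensation, itching and the eye comfort index for tolerability.

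**The concern.** An intention-to-treat set is defined by randomisation. This one is defined by attendance up to about day 6 and possibly also by adherence, both of which tolerability can affect. A subject whose eyes burn may stop the drops, fall below an adherence threshold, be eliminated for intolerance, or miss Visit 2. The outcome under study is then a route out of the analysis of that outcome.

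The direction matters because the plan concludes that the product is safe and tolerable from an absence of difference. Removing early intolerant leavers lowers the observed symptom and sign rates most in the least tolerated arm, and so narrows any true difference. A completer set is therefore not the cautious choice in this design.

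**Working it through.** **1. Which data are lost, by variable**

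| Variable | Post-baseline collection (6.4.3.9, 6.4.4, 6.5) | Effect of leaving before Visit 2 |
|---|---|---|
| Adverse events | Every visit and the safety call; leavers are asked about them (8.1.1) | Kept: all randomised |
| Burning, foreign body sensation, itching | Visits 1, 2 and final; diary after each application | Visit 1 and diary data excluded if 8.3.3 governs |
| Hyperemia, chemosis, staining, pressure, visual capacity | Visits 1, 2 and final | Visit 1 data excluded if 8.3.3 governs |
| Comfort index, goblet cell density, laboratory tests | Final visit only | No value in any case; this loss comes from the schedule |

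For someone who leaves before Visit 1, only a returned diary could add tolerability data.

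**2. Which rule applies**

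The documents do not say whether the visit condition (8.3.3) and the adherence condition (8.3.1) apply together, which set governs which variable, or whether data from eliminated subjects are kept. Section 6.2.3 eliminates below 50% adherence at any visit, while 8.3.1 analyses above 60%. Section 6.3.2.1 gives a bottle-weight formula and then a second method ("The evaluation of the adherence by means of the diary of the subject will be carried out in the following way"), and 8.3.1 does not say which one feeds the 60% rule.

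**3. Rates the documents offer**

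Section 6.6.1 gives 8% adverse events for a preservative-free hyaluronate solution and a 25% increase for probable losses: 24 × 1.25 = 30. That is 6 extra subjects, or 2 per arm. Neither figure is specific to intolerance or to leaving before Visit 2, so the bias cannot be sized from the documents.

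**4. Illustration with assumed counts**

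Inputs: 10 subjects and 20 eyes per arm, because 6.6.1 has both eyes of each subject analysed (60 eyes in total). Symptoms are assumed to be bilateral and are reduced to present/absent. Each affected leaver removes two affected eyes from both numerator and denominator of one arm. The test is Pearson chi-square across three arms without correction: χ² = Σ(O − E)²/E. With 2 df, p = exp(−χ²/2).

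Worked once, for 4/20 v 0/20 v 0/20: E = 4/3 = 1.333 affected and 18.667 unaffected eyes per arm. χ² = [(4 − 1.333)² + 2(1.333)²] × (1/1.333 + 1/18.667) = 10.667 × 0.8036 = 8.571. p = exp(−4.286) = 0.014.

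| Eyes affected, all randomised | χ², p | After affected leavers | χ², p |
|---|---|---|---|
| 4/20 v 0/20 v 0/20 | 8.571, 0.014 | one leaver: 2/18 v 0/20 v 0/20 | 4.603, 0.10 |
| 8/20 v 2/20 v 2/20 | 7.500, 0.024 | one leaver: 6/18 v 2/20 v 2/20 | 4.737, 0.094 |
| same | same | three leavers: 2/14 v 2/20 v 2/20 | 0.193, 0.91 |
| 8/20 v 0/20 v 0/20 | 18.462, 0.0001 | two leavers: 4/16 v 0/20 v 0/20 | 10.769, 0.005 |

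In the three-leaver case the observed rate falls from 40% (8/20) to 14% (2/14). Section 8.3.1 says the comparison of qualitative variables "will be done by creating 2x2 contingency tables". As a single 2x2 table of eyes, 8/20 v 2/20 gives p = 0.028, and 2/14 v 2/20 gives p = 0.70.

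**5. Sensitivity to the unit**

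Counted by subject, different cases cross 0.05. 4/10 v 0/10 v 0/10 moves from p = 0.010 to 0.068 (2/8) after two leavers, whereas by eye it stays significant. 2/10 v 0/10 v 0/10 has p = 0.12 before any exclusion, whereas by eye it starts below 0.05. Per-eye p-values treat paired eyes as independent, and expected counts are small on either unit, so all these values are illustrative only.

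**The case against.** The strongest reply is that a shift in one variable is not a shift in the verdict. Section 8.3.1 requires no difference in all primaries. Adverse events are a primary, are counted in every randomised participant, and section 8.1.1 asks for adverse events and the reason for leaving from anyone who cannot be rebooked. If intolerance is recorded as an adverse event, that variable may still differ and block the conclusion. The rule also asks for no clinical difference, and two withdrawals for intolerance would be visible whatever the p-value. This stands. A reader might infer that the exclusion would lead to an unsafe product being declared safe, but the documents do not show that. The protection has limits: it does not extend to the graded symptoms and signs, and it depends on intolerance being reported as an adverse event.

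A second reply is that exclusion is not certain. Under the adherence rule alone, a subject with good adherence up to Visit 1 might be retained, and section 9.3.1.3 leaves withdrawal after an adverse event to the investigator's opinion. This also stands. A reader might infer that every intolerant subject is dropped, but the text supports only the conditional statement: excluded if the subject leaves before Visit 2 and 8.3.3 governs.

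A third reply is that the assumed rates are high. Section 5.3 reports no adverse reactions with the marketed preserved combination, and section 6.6.1 works from 8%. That is a fair reason to expect few leavers. It does not justify discarding data already collected from those who do leave.

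**Conclusion.** The point holds in conditional form and should be fixed. It is clear from the text that the set labelled intention-to-treat is conditioned on events after randomisation, that only adverse events keep all randomised participants, and that no provision returns early leavers to the symptom and sign primaries. Where 8.3.3 governs, the bias runs towards no difference, and so towards the conclusion that the product is safe and tolerable.

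The size is unknown, and the bias is partial because adverse events can catch the same intolerance. One to three affected leavers in an arm can move a single variable across 0.05 in some assumed patterns and not in others, depending on the comparator rate and the unit of analysis. A changed overall verdict is possible but not demonstrated. The figures assume bilateral symptoms, a binary summary of what the visits record in five categories, and early departure of affected subjects in one arm only.

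**What to change.** 1. Make all randomised subjects who received at least one drop, analysed as randomised, the primary set for every safety and tolerability variable. Use all available post-baseline data, including Visit 1, the diary and data collected before elimination.
2. Report eliminations, early stops with reasons, and missing values by arm.
3. Keep the set defined by Visits 1 and 2 and adherence above 60% as a labelled per-protocol sensitivity analysis, and do not call it intention-to-treat.
4. Reconcile sections 6.2.3, 6.3.2.1, 8.3.1 and 8.3.3: which set governs which variable, whether the two conditions combine, which adherence method feeds the analysis rule, and whether data from eliminated subjects are kept.
5. State that the comfort index, goblet cell density and final laboratory tests have no post-baseline value without a final visit.
6. Optionally, add a sensitivity analysis with a binary summary that counts stopping for intolerance as a failure.

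The cost is SAP wording and one or two extra tables. Visits, elimination criteria and sample size do not change. The fix cannot recover the comfort index, goblet cell density or final laboratory values in subjects without a final visit.
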